6.2. Preparation, Handling, Storage, and Accountability

- 1. The investigator or designee must confirm that appropriate conditions (eg, temperature) have been maintained during transit for all study interventions received and any discrepancies are reported and resolved before use of the study intervention.
- 2. Only participants enrolled in the study may receive study intervention and only authorized site staff may supply, prepare, and/or administer study intervention.
- 3. All study interventions must be stored in a secure, environmentally controlled, and monitored (manual or automated recording) area in accordance with the labeled storage conditions with access limited to the investigator and authorized site staff. At a minimum,

daily minimum and maximum temperatures for all site storage locations must be documented and available upon request. Data for nonworking days must indicate the minimum and maximum temperatures since previously documented upon return to business.

- 4. Any excursions from the study intervention label storage conditions should be reported to Pfizer upon discovery along with actions taken. The site should actively pursue options for returning the study intervention to the labeled storage conditions, as soon as possible. Once an excursion is identified, the study intervention must be quarantined and not used until Pfizer provides permission to use the study intervention. Specific details regarding the excursion definition and information to report for each excursion will be provided to the site in the PCRU's local/site procedures.
- 5. Any storage conditions stated in the SRSD will be superseded by the storage conditions stated on the label.
- 6. Study interventions should be stored in their original containers.
- 7. The investigator, institution, head of the medical institution (where applicable), or authorized site staff is responsible for study intervention accountability, reconciliation, and record maintenance (ie, receipt, reconciliation, and final disposition records), such as the IPAL or sponsor-approved equivalent. All study interventions will be accounted for using a study intervention accountability form/record.
- 8. Further guidance and information for the final disposition of unused study interventions are provided in the PCRU's local/site procedures. All destruction must be adequately documented. If destruction is authorized to take place at the investigator site, the investigator must ensure that the materials are destroyed in compliance with applicable environmental regulations, institutional policy, and any special instructions provided by Pfizer.

Upon identification of a product complaint, notify the sponsor within 1 business day of discovery as described in the PCRU's local/site procedures.

6.2.1. Preparation and Dispensing

Within this protocol, preparation refers to the investigator site activities performed to make the study intervention ready for administration or dispensing to the participant by qualified staff. Dispensing is defined as the provision of study intervention, concomitant treatments, and accompanying information by qualified staff member(s) to a healthcare provider, participant, in accordance with this protocol. Local health authority regulations or investigator site guidelines may use alternative terms for these activities.

Ritlecitinib MR1 and MR2 powder-in-capsules and Ritlecitinib oral solution will be prepared in the CRU by 2 operators, one of whom is a pharmacist. Details of dose preparation will be given in a separate EDR. Prepared doses will be provided in unit dose containers and labeled in accordance with Pfizer regulations and the investigator site's labeling requirements.

6.3. Assignment to study intervention

The investigator will assign participant numbers to the participants as they are screened for the study. Pfizer will provide a randomization schedule to the investigator and, in accordance with the randomization numbers, the participant will receive the study treatment regimen assigned to the corresponding randomization number.

The investigator's knowledge of the treatment should not influence the decision to enroll a particular participant or affect the order in which participants are enrolled.

6.4. Blinding

This is an open-label study.

6.4.1. Blinding of Participants

Participants will be unblinded to their assigned study intervention.

6.4.2. Blinding of Site Personnel

Investigators and other site staff will be unblinded to participants' assigned study intervention.

PCRU pharmacy staff responsible for preparing all study interventions will be unblinded. PCRU site staff providing technical system support to pharmacy staff and supporting blinded laboratory data processes will be unblinded. These site staff providing system support will not be involved in any data collection or clinic floor activities.

6.4.3. Blinding of the Sponsor

As this is an open label study, the sponsor may conduct unblinded reviews of the data during the course of the study for the purpose of safety assessment, facilitating dose escalation decisions, facilitating PK/PD modeling, and/or supporting clinical development.

6.5. Study Intervention Compliance

When the individual dose for a participant is prepared from a bulk supply, the preparation of the dose will be confirmed by a second qualified member of the study site staff.

When participants are dosed at the site, they will receive study intervention directly from the investigator or designee, under medical supervision. The date and time of each dose administered in the clinic will be recorded in the source documents and recorded in the CRF. The dose of study intervention and study participant identification will be confirmed at the time of dosing by a member of the study site staff other than the person administering the study intervention. Study site personnel will examine each participant's mouth to ensure that the study intervention was ingested.

6.6. Dose Modification

Dose modification is not permitted during the study.

6.7. Continued Access to Study Intervention After the End of the Study

No study intervention will be provided to participants at the end of their study participation. It is expected that participants will be treated as required with standard-of-care treatments, as advised by their usual care physician.

6.8. Treatment of Overdose

For this study, any dose of ritlecitinib greater than 800 mg within a 24-hour time period will be considered an overdose.

There is no specific treatment for an overdose.

In the event of an overdose, the investigator should:

- 1. Contact the study medical monitor within 24 hours.
- 2. Closely monitor the participant for any AEs/SAEs and laboratory abnormalities as medically appropriate and follow up until resolution, stabilization, the event is otherwise explained, or the participant is lost to follow-up (as defined in Section 7.3). at least until the next scheduled follow-up.
- 3. Document the quantity of the excess dose as well as the duration of the overdose in the CRF.
- 4. Overdose is reportable to Pfizer Safety only when associated with an SAE.
- 5. Obtain a blood sample for PK analysis within 4 days from the date of the last dose of study intervention if requested by the study medical monitor (determined on a case-by-case basis).

Decisions regarding dose interruptions or modifications will be made by the investigator in consultation with the study medical monitor as needed based on the clinical evaluation of the participant.

6.9. Prior and Concomitant Therapy

Participants will abstain from all concomitant treatments, except for the treatment of adverse events.

Use of prescription or nonprescription drugs and dietary and herbal supplements are prohibited within 7 days or 5 half-lives (whichever is longer) prior to the first dose of study intervention with the exception of moderate/strong CYP3A inducers or inhibitors which are prohibited within 14 days plus 5 half-lives- prior to the first dose of study intervention. Limited use of nonprescription medications that are not believed to affect participant safety or the overall results of the study may be permitted on a case -by -case basis following approval by the sponsor. Acetaminophen/paracetamol may be used at doses of ≤ 1 g/day.

Hormonal contraceptives that meet the requirements of this study are allowed to be used in participants who are WOCBP (see Appendix 4).

All concomitant treatments taken during the study must be recorded with indication, daily dose, and start and stop dates of administration. All participants will be questioned about concomitant treatment at each clinic visit.

Treatments taken within 28 days before the first dose of study intervention will be documented as a prior treatment. Treatments taken after the first dose of study intervention will be documented as concomitant treatments.

7. DISCONTINUATION OF STUDY INTERVENTION AND PARTICIPANT DISCONTINUATION/WITHDRAWAL

7.1. Discontinuation of Study Intervention

It may be necessary for a participant to permanently discontinue study intervention. Reasons for permanent discontinuation of study intervention include the following: treatment-related SAEs, serious infections, and other events as described in Section 5.2.

Discontinuation of study intervention does not represent withdrawal from the study. If study intervention is permanently discontinued, the participant should remain in the study to be evaluated for safety. See the SoA for data to be collected at the time of discontinuation of study intervention and follow-up for any further evaluations that need to be completed.

In the event of discontinuation of study intervention, it must be documented on the appropriate CRF/in the medical records whether the participant is discontinuing further receipt of study intervention or also from study procedures, posttreatment study follow-up, and/or future collection of additional information.

7.1.1. Potential Cases of Acute Kidney Injury

Participants exposed to IMP demonstrating transient or sustained increase in Screat (with decrease in Screat-based eGFR or eCrCl) require expedited evaluation to differentiate AKI from DICI. DICI is defined as transporter-mediated effect related to altered renal tubular creatinine handling without histological injury.

AKI may be due to one or more types of injury, including DIKI. Differentiation of DIKI from other causes of AKI and from DICI may require clinical, radiographic, histopathologic, and laboratory assessments, as well as nephrology consultation.

Follow-up Assessments

The participant should return to the site for evaluation as soon as possible, preferably within 48 hours of awareness of the abnormal results.

Evaluation should include physical examination, laboratory tests, detailed medical and surgical history, review of all medications (including recreational drugs and supplements

[herbal]), family history, sexual history, travel history, blood transfusion, and potential occupational exposure to chemicals.

Laboratory assessments should include simultaneous serum cystatin C (Scys) and serum creatinine (Screat) tests. Estimates of eGFR, eCrCl and Screat-based eGFR and combined Screat-Scys-based eGFR should also be derived using the appropriate equation described in Appendix 7: Kidney Safety: Monitoring Guidelines.

Assessments of urine albumin-to-creatinine ratio or urine volume may also be performed as appropriate.

Differentiating Acute Kidney Injury from DICI

A confirmed Screat increase is defined as:

- (i) \geq 0.3 mg/dL (\geq 26.5 μ mol/L) within 48 hours OR
- (ii) confirmed Screat increase ≥ 1.5 times baseline (known or suspected to have occurred within the prior 7 days).

Based on the assessments performed, suspected AKI (including DIKI) may be differentiated from DICI as follows.

Adult participants

Addit participants		
	AKI (including DIKI) Any one of the below	DICI
Scys & Screat	Simultaneous, confirmed serum cystatin C (Scys) increase and confirmed Screat increase	Confirmed Screat increase without confirmed increase in reflex Scys AND Confirmed Screat-based eGFR
eGFR	Decrease in Screat-based eGFR and combined Screat-Scys-based eGFR (when available)	decrease without confirmed combined Screat-Scys-based eGFR decrease.
Albuminuria or proteinuria	Confirmed albuminuria increase (see Appendix 7 for Grades A1 to A3 quantitation)	
Urine volume	Urine volume <0.5 mL/kg/h for 6 consecutive hours	

Regardless of the presence or absence of increase in Screat, DIKI and other causes of AKI may be suspected if either there is (i) new-onset or worsening albuminuria or proteinuria are detected or (ii) urine volume (if measured) is <0.5 mL/kg/h for 6 consecutive hours).

All confirmed cases of clinically relevant decrease in kidney function should be considered potential cases of DIKI if no other reason for the kidney function abnormalities has been found.

7.1.2. Liver Injury

A participant who meets the criteria as described in Appendix 6 will be withdrawn from study intervention.

7.2. Participant Discontinuation/Withdrawal From the Study

A participant may withdraw from the study at any time at their own request. Reasons for discontinuation from the study include the following:

- Refused further follow-up;
- Lost to follow-up;
- Death;
- Study terminated by sponsor;
- Participant meeting protocol specified criteria for discontinuation.

At the time of discontinuation from the study, if possible, an early discontinuation visit should be conducted. See the SoA for assessments to be collected at the time of study discontinuation and follow-up and for any further evaluations that need to be completed.

The early discontinuation visit applies only to participants who are enrolled/randomized and then are prematurely withdrawn from the study. Participants should be questioned regarding their reason for withdrawal.

The participant will be permanently discontinued from the study intervention and the study at that time.

If a participant withdraws from the study, they may request destruction of any remaining samples taken and not tested, and the investigator must document any such requests in the site study records and notify the sponsor accordingly.

If the participant withdraws from the study and also withdraws consent (see Section 7.2.1) for disclosure of future information, no further evaluations will be performed and no additional data will be collected. The sponsor may retain and continue to use any data collected before such withdrawal of consent.

7.2.1. Withdrawal of Consent

Participants who request to discontinue receipt of study intervention will remain in the study and must continue to be followed for protocol- specified follow- up procedures. The only

exception to this is when a participant specifically withdraws consent for any further contact with them or persons previously authorized by the participant to provide this information. Participants should notify the investigator in writing of the decision to withdraw consent from future follow-up, whenever possible. The withdrawal of consent should be explained in detail in the medical records by the investigator, as to whether the withdrawal is only from further receipt of study intervention or also from study procedures and/or posttreatment study follow-up, and entered on the appropriate CRF page. In the event that vital status (whether the participant is alive or dead) is being measured, publicly available information should be used to determine vital status only as appropriately directed in accordance with local law.

7.3. Lost to Follow-Up

A participant will be considered lost to follow-up if the participant repeatedly fails to return for scheduled visits and is unable to be contacted by the study site.

The following actions must be taken if a participant fails to return to the clinic for a required study visit:

- The site must attempt to contact the participant and reschedule the missed visit as soon as possible. Counsel the participant on the importance of maintaining the assigned visit schedule and ascertain whether the participant wishes to and/or should continue in the study;
- Before a participant is deemed lost to follow-up, the investigator or designee must make every effort to regain contact with the participant (where possible, 3 telephone calls and, if necessary, a certified letter to the participant's last known mailing address or local equivalent methods). These contact attempts should be documented in the participant's medical record;
- Should the participant continue to be unreachable, the participant will be considered to have withdrawn from the study.

8. STUDY ASSESSMENTS AND PROCEDURES

8.1. Administrative Procedures

The investigator (or an appropriate delegate at the investigator site) must obtain a signed and dated ICD before performing any study-specific procedures.

Study procedures and their timing are summarized in the SoA. Protocol waivers or exemptions are not allowed.

Adherence to the study design requirements, including those specified in the SoA, is essential and required for study conduct.

All screening evaluations must be completed and reviewed to confirm that potential participants meet all eligibility criteria. The investigator will maintain a screening log to

record details of all participants screened and to confirm eligibility or record reasons for screening failure, as applicable.

Participants will be screened within 28 days prior to administration of the study intervention to confirm that they meet the study population criteria for the study. If the time between screening and dosing exceeds 28 days because of unexpected delays (eg, delayed drug shipment), then participants do not require rescreening if the laboratory results obtained prior to first dose administration meet eligibility criteria.

A participant who qualified for this protocol but did not enroll from an earlier cohort/group may be used in a subsequent cohort/group without rescreening, provided laboratory results obtained prior to the first dose administration meet eligibility criteria for this study. In addition, other clinical assessments or specimen collections, eg, retained research samples, may not need to be repeated, as appropriate.

Every effort should be made to ensure that protocol- required tests and procedures are completed as described. However, it is anticipated that from time to time there may be circumstances outside the control of the investigator that make it unfeasible to perform the test. In these cases, the investigator must take all steps necessary to ensure the safety and well-being of the participant. When a protocol- required test cannot be performed, the investigator will document the reason for the missed test and any corrective and preventive actions that they have taken to ensure that required processes are adhered to as soon as possible. The study team must be informed of these incidents in a timely manner.

For samples being collected and shipped, detailed collection, processing, storage, and shipment instructions and contact information will be provided to the investigator site prior to initiation of the study.

The total blood sampling volume for individual participants in this study is approximately 150 mL. The actual collection times of blood sampling may change. Additional blood samples may be taken for safety assessments at times specified by Pfizer, provided the total volume taken during the study does not exceed 550 mL during any period of 60 consecutive days.

To prepare for study participation, participants will be instructed on the information in the Lifestyle Considerations and Concomitant Therapy sections of the protocol.

8.2. Efficacy Assessments

Efficacy parameters are not evaluated in this study.

8.3. Safety Assessments

Planned time points for all safety assessments are provided in the SoA. Unscheduled safety measurements may be obtained at any time during the study to assess any perceived safety issues.

8.3.1. Physical Examinations

A complete physical examination will include, at a minimum, head, ears, eyes, nose, mouth, skin, heart and lung examinations, lymph nodes, and gastrointestinal, musculoskeletal, and neurological systems.

A brief physical examination will include, at a minimum, assessments of general appearance, the respiratory and cardiovascular systems, and participant- reported symptoms.

Physical examinations may be conducted by a physician, trained physician's assistant, or nurse practitioner as acceptable according to local regulation.

Height and weight will also be measured and recorded as per the SoA. For measuring weight, a scale with appropriate range and resolution is used and must be placed on a stable, flat surface. Participants must remove shoes, bulky layers of clothing, and jackets so that only light clothing remains. They must also remove the contents of their pockets and remain still during measurement of weight.

Physical examination findings collected during the study will be considered source record and will not be required to be reported, unless otherwise noted. Any untoward physical examination findings that are identified during the active collection period and meet the definition of an AE or SAE (Appendix 3) must be reported according to the processes in Sections 8.4.1 to 8.4.3.

8.3.2. Vital Signs

8.3.2.1. Blood Pressure and Pulse Rate

Supine BP will be measured with the participant's arm supported at the level of the heart, and recorded to the nearest mm Hg after approximately 5 minutes of rest. The same arm (preferably the dominant arm) will be used throughout the study. Participants should be instructed not to speak during measurements.

The same properly sized and calibrated BP cuff will be used to measure BP each time. The use of an automated device for measuring BP and pulse rate is acceptable; however, when done manually, pulse rate will be measured in the brachial/radial artery for at least 30 seconds. When the timing of these measurements coincides with a blood collection, BP and pulse rate should be obtained prior to the nominal time of the blood collection.

Additional collection times, or changes to collection times, of BP and pulse rate will be permitted, as necessary, to ensure appropriate collection of safety data.

Any untoward vital sign findings that are identified during the active collection period and meet the definition of an AE or SAE (Appendix 3) must be reported according to the processes in Sections 8.4.1 to 8.4.3.

8.3.2.2. Temperature

Body temperature will be measured. No eating, drinking, or smoking is allowed for 15 minutes prior to the measurement.

8.3.3. Electrocardiograms

Standard 12-lead ECGs will be collected at times specified in the SoA section of this protocol using an ECG system that automatically calculates the HR and measures PR, QT, QTcF, and QRS intervals. All scheduled ECGs should be performed after the participant has rested quietly for at least 5 minutes in a supine position.

To ensure safety of the participants, a qualified individual at the investigator site will make comparisons to baseline measurements, defined as pre-dose ECG of the current period. Additional ECG monitoring will occur if a) a postdose QTc interval is increased by ≥60 msec from the baseline **and** is >450 msec; or b) an absolute QTc value is ≥500 msec for any scheduled ECG. If either of these conditions occurs, then 2 additional ECGs will be collected approximately 2 to 4 minutes apart to confirm the original measurement. If the QTc values from these repeated ECGs remain above the threshold value, then a single ECG must be repeated at least hourly until QTc values from 2 successive ECGs fall below the threshold value that triggered the repeat measurement.

If a) a postdose QTcF interval remains \geq 60 ms from the baseline and is >450 ms; or b) an absolute QT value is \geq 500 ms for any scheduled ECG for greater than 4 hours (or sooner, at the discretion of the investigator); or c) QTcF value get progressively longer, the participant should undergo continuous ECG monitoring. A cardiologist should be consulted if QTcF values do not return to less than the criteria listed above after 8 hours of monitoring (or sooner, at the discretion of the investigator).

In some cases, it may be appropriate to repeat abnormal ECGs to rule out improper lead placement as contributing to the ECG abnormality. It is important that leads be placed in the same positions each time in order to achieve precise ECG recordings. If a machine-read QTc value is prolonged, as defined above, repeat measurements may not be necessary if a qualified medical provider's interpretation determines that the QTcF values are in the acceptable range.

ECG values of potential clinical concern are listed in Appendix 8.

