3 04:30	Days Relative to Day 1	Day -28 to Day -2	Day -	Day 1	Day 2	Day 3	28-35 Days after last dose in Period 4												
202,	Study Day	-28 to -2	-1	1	2	3	4	5	6	7	8	9	10	11	12				
On: 15-Nov-	Pregnancy test (WOCBP only)	X	X															•	Given that the participant will be confined in CRU for the entire study, if tested negative on admission, no further test is needed.
pproved\Approved	Contraception check	Х	X													X	X	•	The contraception check is to confirm that contraception, if applicable, is used consistently and correctly.
Srov	Review prior or concomitant treatments and medications	X	X	\rightarrow	X	X													
ce19\Apr	FSH (WONCBP only)	X																•	Serum FSH for confirmation of postmenopausal status only
$\tilde{\infty}$	Urine drug testing	X	X																
7e19f2	Supine 12-lead single ECG	X		X			X			X			X		X		X		Day 1 ECG to be done pre-dose.

Visit Identifier Abbreviations used in this table may be found in Appendix 9: Abbreviations.	Screening									Trea	itment	Perio	d				Notes
Days Relative to Day 1 Study Day			Peri	od 1		Pe	riod 2		P	eriod	3		Period	14	Follow-up Contact	Early Termination/ Discontinuation	Follow-up contact will occur by telephone and must occur 28 to 35 days after the last administration of ritlecitinib.
Days Relative to Day 1	Day -28 to Day -2	Day -	Day 1	Day 2	Day 3	28-35 Days after last dose in Period 4											
Study Day	-28 to -2	-1	1	2	3	4	5	6	7	8	9	10	11	12			
Supine blood pressure, pulse rate and temperature	X		X			X			X			X		X		Х	Day 1 vital signs are collected prior to pre- dose (baseline) blood drawn.
HIV, HBsAg, HBcAb, HCVAb QuantiFERON®TB Gold test or equivalent	X																If HBsAg is negative and HBcAb is positive, HBsAb should be evaluated.
QuantiFERON®TB Gold test or equivalent	X																
Study intervention administration Pharmacokinetic blood sampling			X			X			X			X					Please refer to Section 5.3.2 for details regarding dosing under fed and fasted state.
Pharmacokinetic blood sampling			X	X	X	X	X	X	X	X	X	X	X	X		Х	PK sample collection will be done pre-dose and at times post-dose as shown in Table 1 below.

	Visit Identifier Abbreviations used in this	Screening									Trea	tment	Perio	d				Notes
	table may be found in																	

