- 18. Standard 12-lead ECG that demonstrates clinically relevant abnormalities that may affect participant safety or interpretation of study results (eg, QTcF > 450 ms, complete LBBB, signs of an acute or indeterminate- age myocardial infarction, ST-T interval changes suggestive of myocardial ischemia, second- or third- degree AV

block, or serious bradyarrhythmias or tachyarrhythmias). If QTcF exceeds 450 ms, or QRS exceeds 120 ms, the ECG should be repeated twice, and the average of the 3 QTcF or QRS values should be used to determine the participant's eligibility. Computer interpreted- ECGs should be overread by a physician experienced in reading ECGs before excluding a participant.

- 19. Participants with ANY of the following abnormalities in clinical laboratory tests at screening or Day -1, as assessed by the study-specific- laboratory and confirmed by a single repeat test, if deemed necessary:
 - AST or ALT level $> 1.5 \times ULN$;
 - Total bilirubin level >1.5 × ULN; participants with a history of Gilbert's syndrome may have direct bilirubin measured and would be eligible for this study provided the direct bilirubin level is ≤ ULN;
 - Hemoglobin level <120 g/L (12.0 g/dL);
 - Platelet count $<150 \times 10^9/L (150,000 \text{ cells/mm}^3);$
 - ANC $<1.2 \times 10^9/L$ (1200 cells/mm³);
 - ALC $< 0.8 \times 10^9 / L (800 \text{ cells/mm}^3);$
 - eGFR <60 mL/minute/1.73 m² based on the CKD-EPI equation

In the opinion of the investigator or Pfizer (or designee), have any clinically significant laboratory abnormality that could affect interpretation of study data or the participant's participation in the study.

Other Exclusion Criteria:

- 20. History of alcohol abuse or binge drinking and/or any other illicit drug use or dependence within 6 months of Screening. Binge drinking is defined as a pattern of 5 (male) and 4 (female) or more alcoholic drinks in about 2 hours. As a general rule, alcohol intake should not exceed 14 units per week (1 unit = 8 ounces (240 mL) beer, 1 ounce (30 mL) of 40% spirit, or 3 ounces (90 mL) of wine).
- 21. Blood donation (excluding plasma donations) of approximately 1 pint (500 mL) or more within 60 days prior to dosing.
- 22. Use of tobacco/nicotine containing products in excess of 5 cigarettes/day.
- 23. History of severe allergic or anaphylactic reactions.

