9.3.3.1. Electrocardiogram Analyses

Changes from baseline for the ECG parameters QT interval, heart rate, QTc interval, PR interval, and QRS complex will be summarized by treatment and time.

The number (%) of participants with maximum postdose QTc values and maximum increases from baseline in the following categories will be tabulated by treatment:

Safety QTc Assessment

Degree of Prolongation	Mild (msec)	Moderate (msec)	Severe (msec)
Absolute value	>450-480	>480-500	>500
Increase from baseline		30-60	>60

In addition, the number of participants with uncorrected QT values >500 msec will be summarized.

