10.8. Appendix 8: ECG Findings of Potential Clinical Concern

ECG Findings That May Qualify as AEs

- Marked sinus bradycardia (rate <40 bpm) lasting minutes.
- New PR interval prolongation >280 ms.
- New prolongation of QTcF to >480 ms (absolute).
- New prolongation of QTcF by >60 ms from baseline.
- New-onset atrial flutter or fibrillation, with controlled ventricular response rate: ie, rate <120 bpm.
- New-onset type I second-degree (Wenckebach) AV block of >30-second duration.
- Frequent PVCs, triplets, or short intervals (<30 seconds) of consecutive ventricular complexes.

ECG Findings That May Qualify as SAEs

- QTcF prolongation >500 ms.
- Absolute value of QTcF > 450 ms AND QTcF change from baseline >60 ms.
- New ST-T changes suggestive of myocardial ischemia.
- New onset- LBBB (QRS complex>120 ms).
- New onset- right bundle branch block (QRS complex>120 ms).
- Symptomatic bradycardia.
- Asystole
 - In awake, symptom-free- participants in sinus rhythm, with documented asystolic pauses ≥3 seconds or any escape rate <40 bpm, or with an escape rhythm that is below the AV node;
 - In awake, symptom-free- participants with atrial fibrillation and bradycardia with 1 or more asystolic pauses of at least 5 seconds or longer.
- Atrial flutter or fibrillation, with rapid ventricular response rate: rapid = rate >120 bpm.

- Sustained supraventricular tachycardia (rate >120 bpm) ("sustained" = short duration with relevant symptoms or lasting >1 minute).
- Ventricular rhythms >30 seconds' duration, including idioventricular rhythm (HR <40 bpm), accelerated idioventricular rhythm (HR >40 bpm to <100 bpm), and monomorphic/polymorphic ventricular tachycardia (HR >100 bpm [such as torsades de pointes]).
- Type II second-degree (Mobitz II) AV block.
- Complete (third-degree) heart block.

ECG Findings That Qualify as SAEs

- Change in pattern suggestive of new myocardial infarction.
- Sustained ventricular tachyarrhythmias (>30-seconds duration).
- Second- or third degree- AV block requiring pacemaker placement.
- Asystolic pauses requiring pacemaker placement.
- Atrial flutter or fibrillation with rapid ventricular response requiring cardioversion.
- Ventricular fibrillation/flutter.
- At the discretion of the investigator, any arrhythmia classified as an adverse experience.

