### **3.5.4. ECG**

Single supine 12-lead ECG will be taken at all time points listed in the Schedule of Activities given in the protocol. For calculation of change from baseline for Periods 1 - 3, the baseline of Period 4 is used as post-baseline; for Period 4, the measurement on Day 3 will be used as the post-baseline measurement.

The QT, QTc, PR, QRS and heart rate will be recorded at each assessment time.

If not supplied, QTcF will be derived using Fridericia's heart rate correction formula:

$$QTcF = QT / (RR)^{1/3} \quad \text{where RR} = 60/\text{HR} \text{ (if not provided)}$$

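### The absolute limb of the continuous-ECG-monitoring rule is set on QT where the rest of the rule uses QTcF, so its 500 ms limit shifts with heart rate

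*Protocol*

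**What the plan says.** Protocol Section 8.3.3 has two linked steps.

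- **Repeat ECGs.** Two further ECGs are taken if postdose QTc has risen by at least 60 msec from baseline and exceeds 450 msec, or if "an absolute QTc value is ≥500 msec for any scheduled ECG". If the repeats confirm it, "a single ECG must be repeated at least hourly until QTc values" fall below the triggering threshold on two successive tracings. Baseline here is the pre-dose ECG of the current period.
- **Continuous monitoring.** Limb (a) is a sustained QTcF rise of at least 60 ms with QTcF above 450 ms. Limb (b) reads "or b) an absolute QT value is" at or above 500 ms for more than 4 hours, or sooner at the investigator's discretion. Limb (c) is progressive lengthening of QTcF. The cardiologist referral that follows asks whether QTcF has come back below the listed criteria.

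Elsewhere, Appendix 8 (Section 10.8) lists "QTcF prolongation >500 ms" as a possible SAE and states its other QT-interval limits in QTcF. The ECG exclusion criterion in Section 5.2 also uses it: "If QTcF exceeds 450 ms" the tracing is repeated. Raw QT appears explicitly in Section 9.3.3.1, where "the number of participants with uncorrected QT values >500 msec will be summarized". That is a descriptive count and triggers no monitoring.

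**The concern.** Limb (b) repeats the structure and the 500 ms limit of the repeat-ECG trigger, but on a different interval. Section 8.3.3 lists QT and QTcF as separate outputs of the ECG system, so the two terms cannot be read as synonyms.

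Read literally, the rule has three faults. Its absolute limit moves with heart rate. It does not match the trigger that feeds it. It also leaves the cardiologist referral, which is framed in QTcF, with no absolute 500 ms QTcF criterion to apply.

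At stake is when a participant moves from hourly to continuous ECG monitoring. At faster rates the literal rule can leave out someone whose QTcF stays just above 500 ms. At slower rates it could call for monitoring below QTcF 500 ms, which is the cautious direction.

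**Working it through.** The plan states no figure of its own to reproduce.

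**Inputs.** The formula QTcF = QT / (RR)^(1/3) with RR = 60/HR is from SAP Section 3.5.4. The 500 ms limit and the limb (a) conditions (rise of at least 60 ms, QTcF above 450 ms) are from Protocol Section 8.3.3. The 450 ms entry limit is from Protocol Section 5.2.

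**Step 1: what QT 500 ms means in QTcF.** QTcF = 500 / (60/HR)^(1/3). The two are equal only when 60/HR = 1, that is at 60 bpm.

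| HR (bpm) | QTcF when QT = 500 ms | QT when QTcF = 500 ms |
|---|---|---|
| 45 | 454.3 | 550.3 |
| 50 | 470.5 | 531.3 |
| 55 | 485.7 | 514.7 |
| 60 | 500.0 | 500.0 |
| 75 | 538.6 | 464.2 |
| 100 | 592.8 | 421.7 |

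**Step 2: what limb (a) already covers.** Limb (a) is met once QTcF reaches baseline + 60 (and is above 450). A QTcF of 500 ms or more therefore escapes limb (a) only in the band from 500 up to, but not including, baseline + 60.

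| Pre-dose QTcF of the period | Band not covered by (a) |
|---|---|
| 440 or less | none (440 + 60 = 500) |
| 445 | 500 to 505 |
| 450 | 500 to 510 |
| 460 | 500 to 520 |

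The last row needs a pre-dose value above the 450 ms entry limit.

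**Step 3: when literal limb (b) misses that band.** A given QTcF has QT below 500 ms when HR > 60 × (QTcF/500)^3. For QTcF 510 this is 60 × (510/500)^3 = 60 × 1.02^3 = 63.7 bpm. Above 63.7 bpm the whole 500 to 510 band has QT below 500 ms. At 75 bpm, QTcF 500 to 510 corresponds to QT 464.2 to 473.4 ms.

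**Step 4: how often the rule could apply.** The Schedule of Activities note says "Day 1 ECG to be done pre-dose". Apart from early termination, the only postdose ECG scheduled within a period is on Day 3 of Period 4. SAP Section 3.5.4 reflects this: "for Period 4, the measurement on Day 3 will be used as the post-baseline measurement".

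**The case against.** The strongest reply is that this is a one-word slip that a trained reader would resolve. The preceding paragraph sets the same limit on QTc, and the cardiologist sentence treats the listed criteria as QTcF criteria. That supports the reading that QTcF was meant, but it does not make the written threshold right.

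A second reply is that raw QT may have been intended, since Section 9.3.3.1 counts raw QT above 500 msec. This cannot be wholly excluded. However, that section labels the interval as uncorrected, which limb (b) does not. The hourly ECGs that would show persistence beyond 4 hours also start and stop on QTc.

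The third reply is about size, and it stands. To be missed, a participant needs a pre-dose QTcF above 440 ms, a rise below 60 ms, a sustained QTcF of at least 500 ms, a heart rate above 60 bpm, no progressive lengthening, no use of investigator discretion, and staff who apply limb (b) literally. Hourly ECGs continue even then. The slow-rate discrepancy is largely theoretical: with QTc below 500 ms and a rise below 60 ms, no repeat series begins. About 12 healthy participants take single 100 mg doses, and Protocol Section 4.3 reports no clinically significant ECG changes in the earlier studies it cites, with single doses up to 800 mg.

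**Conclusion.** The concern holds. As written, limb (b) sets its limit on an interval that disagrees with its own trigger, the neighbouring limbs, the referral rule and Appendix 8. A drafting slip is by far the better reading.

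This is a minor but worthwhile correction to an operative safety rule. The uncovered band is at most 10 ms wide (QTcF 500 to 510) when the period's pre-dose QTcF is within the 450 ms entry limit. It is wider only when that baseline is higher. These sizes assume that the unspecified QTc in the trigger means QTcF, the only corrected interval the named system reports, and that limb (b) is applied literally. Only the step from hourly to continuous monitoring is affected. The PK endpoints, their analyses and the sample size are untouched.

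**What to change.** In limb (b) of the continuous-monitoring rule in Protocol Section 8.3.3, replace the absolute QT value with an absolute QTcF value and leave the limit at 500 ms. The limit is then the same at every heart rate and agrees with the repeat-ECG trigger.

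For consistency, QTc can be changed to QTcF throughout Section 8.3.3. That is tidying and is not needed to correct the rule.

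The cost is a wording change in one protocol section. No new measurement, visit or analysis is required.
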